12.9 Analysis of Secondary Endpoint: Physical Function

To examine strength levels (kilograms lifted for chest press, leg press, seated row and leg extension), cardio-respiratory exercise capacity (oxygen consumption and workload achieved), and functional performance (time in seconds to complete 400m walk test) between groups at 0, 6, 12, 18 and 24 months when performed, the two-sample Wilcoxon rank sum test and two-sample t-test for continuous measurements will be used. To determine if changes in strength, cardiorespiratory exercise capacity and functional performance is different

between the two groups over time, we will use generalised linear mixed models for repeated measures, where group, strata and covariates will be considered as fixed effects, and time will be considered the repeated measure. In order to complete this as an intention to treat analysis, patients with missing data due to failing health or death will be run multiple ways, including assigned levels of physical function across metrics described, and using last observation carried forward.

12.10 Analysis of Secondary Endpoint: Quality of Life

To assess QOL scores (overall QOL, physical wellbeing, social/family wellbeing, emotional wellbeing, functional wellbeing, prostate specific concerns, fatigue, health status) between groups at 6, 12, 18, and 24 months, the two-sample Wilcoxon rank sum test and two-sample t test for continuous measurements will be used. To determine if the change in QOL is different between the two groups over time, we will use generalised linear mixed models for repeated measures for each QOL score with appropriate link function and group, strata and covariates considered as fixed effects, and time considered as the repeated measure. For the EQ5D analyses (QOL utility), we will compare area under the curve. We will consider one value set and country-specific value sets. In the absence of a country-specific value set, a set of values for a population that most closely approximates that country will be used. In order to complete this as an intention to treat analysis, patient with missing data due to failing health or death will be run multiple ways, including assigning scores of zero quality of life and using last observation carried forward.

[figure not shown]
12.11 Other Secondary Analyses

12.11.1 Associations between Circulating Metabolic Biomarkers and OS

We will use multivariate Cox Proportional Hazards regression to examine whether circulating levels of inflammatory and energy metabolism biomarkers are associated with OS, adjusting for potential confounding factors and stratifying by intervention arm, treatment status at registration, and study site. Patients alive at the end of follow-up will be censored on the date of last contact (or, if no contact after the baseline visit, at the date of randomisation + 1 day). We will examine baseline levels as well as update levels over time using assessments at cycles 6, 12, and 24. The biomarkers will be modelled categorically and continuously, as appropriate. Biomarker assessment at baseline and 6 months are funded. Additional funding will be acquired for investigation of additional time points.

12.11.2 Analyses to Explore whether Metabolic Markers Mediate Hypothesized Relation between Exercise and OS

We will explore to what extent the hypothesized benefits in cancer-specific mortality in the exercise group are mediated by changes in inflammatory, energy metabolism, or androgen biomarker levels using a mediation analysis as developed by Vanderweele et al.^{49,50} The mediation analysis will allow us to estimate the proportion of the effect of the exercise intervention on prostate cancer mortality (Y) that is mediated through the biomarkers of interest ($A \rightarrow M \rightarrow Y$), and how much is explained by other causal pathways ($A \rightarrow Y$) (see graphic below).

A is the exposure (exercise group)
M is the mediator (e.g. insulin, IGF, T)
Y is the outcome (mortality)

The causal direct and indirect effect measures can be calculated using Cox proportional hazards regression. The statistical analysis can be implemented using a publically-available SAS macro; moreover, it allows us to estimate these effects even if exercise and the biomarker levels interact.

12.11.3 Per Protocol Analyses

Secondarily, we will conduct analyses using a per-protocol analysis to investigate the possibility of a dose

response or threshold effect. Participants who attend 80% or more of the supervised exercise sessions will be considered to have complied with the protocol.

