6.1.5 Missed sessions

Missed sessions should be rescheduled within the same week, if possible, while allowing at least 48 hours between resistance exercise sessions. Three sessions total (supervised and self-managed sessions) are recommended per week; however up to 3 sessions can be recovered (added) per week if missed in other weeks, totalling a maximum of 6 sessions within one week. The total number of supervised sessions and self-managed exercise sessions should remain the same as originally planned for in Year 1. When recovering missed sessions in a given week, we strongly advise to add 1 additional session per week (totalling 4 exercise sessions) where feasible, so as to not overwhelm the patient. Supervised sessions can occur during the week, which might require self-managed sessions to be moved to a mid-week and/or weekend day to facilitate recovering missed sessions. In the event that more than one missed session is being recovered in a given week, you may reduce volume/intensity in collaboration with the exercise coordination centre to prevent patient overreach. Incorporating additional exercises into a scheduled session to make up missed exercises is allowed and should be discussed with the ECC.

Exacerbation of symptoms such as fatigue should not result in missed sessions, as each training session can be adjusted (auto-regulated) to the patient's current condition on that day. Attendance will be defined as the number of in-person exercise sessions attended divided by the total number of planned supervised sessions. Exercise physiologists/trainers, leading the intervention will guide modification of the prescribed protocol based on the participant's capacity and perception of effort at the time of presentation to each exercise session in line with the principles of auto-regulated training outlined above. The number of missed sessions per participant and the reasons for missing sessions must be recorded and reported. If a participant misses an exercise session, they will be contacted by the research team to determine the reason and to reschedule the session. Every effort must be made by the research team to reschedule missed sessions or add extra exercise to current sessions in order to meet exercise targets.

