Patients are permitted to take holidays however must commit to self-management of exercise during this period. During pre-planned or spontaneous holidays for patients (while on-trial), and/or due to unforeseen circumstances precluding attendance to a supervised session (such as an illness to spouse, or conflicting medical appointment), patients may complete a self-managed session under the strict guidance and overview of the site's research coordinator and exercise physiologist (to be recorded). If this occurs, a self-managed session replacing a supervised session in this way must be recorded in REDCap. If no session is performed to recover the missed session (without any adverse event, or other justifiable reason), this will be recorded in REDCap. During holidays, if patients do not have access to exercise facilities or equivalent items of use, these can be recovered during subsequent weeks within the Year it occurs (as is the definition of autoregulation; to ensure the overall program is upheld). This will be monitored by the Study and Exercise Coordination Centres during routine monitoring visits.

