10.0 PRIMARY ENDPOINT CRITERIA FOR OVERALL SURVIVAL

Patients will be followed for death a minimum of 36 months after randomisation. Overall survival will be measured from the time of randomisation until death. Medical records and death certificates will be reviewed every 6 months to obtain survival status. Country-specific mortality status databases will also be searched annually; cause of death will be determined through review of medical and death records. Patients will be contacted once a year, and follow up with next of kin then alternate contact, if needed, if we do not hear from them.

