12.2 Power and Sample Size for Primary Endpoint

This is a 1:1 randomised controlled trial in men with MCRPC. Registered and eligible participants will be

randomised with equal probability to one of two intervention regimens: supervised exercise for 12 cycles tapering to self-management for 12 cycles with psychosocial support or psychosocial support alone. We will stratify by whether the men are on active therapy or not at the time of registration (yes/no) and study site. A total of 866 men will enrol in this study to ensure at least 412 men evaluable for OS in each arm.

Null hypothesis (H_0)= There is no difference in OS between patients randomised to the exercise intervention plus psychosocial support vs psychosocial support alone.

Alternate hypothesis (H_A) = There is a difference in OS between patients randomised to the exercise intervention plus psychosocial support vs psychosocial support alone.

Considering a total enrolment period of 36-months and minimum 36 months follow-up for each patient after enrolment; assuming survival time follows an exponential distribution; and assuming a median OS survival of 33.5 months in the control arm, the sample size required to detect a hazard ratio (HR) of 0.78 with 80% power at significance level of 0.05 is 824, 412 men in each arm. Accounting for up to 5% of patients with missing data on OS, we aim to enrol 866 men. If we consider non-compliance of 10% in the intervention arm, which equates to 371 patients in the intervention arm who are compliant, this provides 77.7% power to detect an HR of 0.78, when comparing the 371 compliant patients with the 412 patients in the control arm at the significance level of 0.05.

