12.4 Analysis of Primary Endpoint

The primary endpoint for the study is OS (defined in Section 10). An intent-to-treat approach will be used to analyse OS. Patients alive at the end of follow-up will be censored on the date of last contact (or, if no contact after the baseline visit, at the date of randomisation + 1 day). Kaplan-Meier methods will be used to estimate the median OS for each treatment arm as well as the 1-year, 2-year, and 3-year OS rates and corresponding 95% confidence intervals. A two-sided log-rank test, stratified by treatment status (on treatment Y/N) and study site, will be used to assess the effect of the intervention. Un-stratified log-rank tests will be examined as sensitivity analyses. Cox proportional-hazard regression models will be used to estimate the hazard ratio and its 95% confidence interval to quantify the effect of the intervention on OS, adjusting for stratification factor(s). First, the base model will be evaluated and then other potential confounding factors will be considered. We will also conduct secondary analyses with consideration for non-compliance and the number of supervised sessions completed.

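### The attendance-based survival analyses name no landmark, so men must survive to be counted as compliers; separately, the only power figure allowing for non-compliance is not for the intent-to-treat test.

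*Combined protocol and SAP*

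**What the plan says.** **Attendance analyses.** Section 12.4 analyses OS by intent-to-treat ("An intent-to-treat approach will be used to analyse OS") and then adds: "We will also conduct secondary analyses with consideration for non-compliance and the number of supervised sessions completed". Section 12.11.3 gives the compliance rule, "Participants who attend 80% or more of the supervised exercise sessions will be considered to have complied with the protocol", without naming an endpoint or a comparator; its purpose is to look for a dose response or threshold.

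The pieces needed to apply the rule are elsewhere:
- Section 10: "Overall survival will be measured from the time of randomisation until death".
- Section 6.1.5: "Attendance will be defined as the number of in-person exercise sessions attended divided by the total number of planned supervised sessions".
- Section 6.1 plans 88 supervised sessions in Year 1, on condition that no adverse event limits them. The original programme is three a week in weeks 1-4, two a week in weeks 5-36 and one a week in weeks 37-48.
- Section 6.1.8 adds a supervised session about once per cycle from Cycle 12.

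No section gives a landmark, a time-dependent definition of attendance, or a rule for classifying men who die before the supervised period ends.

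**Power.** Section 12.2 gives 80% power for 412 v 412 at HR 0.78. Assuming 10% non-compliance in the exercise arm, it says "this provides 77.7% power to detect an HR of 0.78, when comparing the 371 compliant patients with the 412 patients in the control arm". It starts from "Considering a total enrolment period of 36-months and minimum 36 months follow-up for each patient after enrolment", while the synopsis has 60 months of enrolment and section 17.6 has 5 years.

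**The concern.** Compliance is known only after months of follow-up, but the survival clock starts at randomisation. A man classed as a complier has, by definition, lived long enough to attend the required sessions. Controls face no such condition, and all their early deaths count. This is immortal-time bias, and it favours exercise. A secondary complier or sessions-completed result could therefore show a survival benefit, or an apparent dose response, where there is none.

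The power question is smaller. The 77.7% removes the non-compliers and leaves the HR at 0.78. The primary test keeps those men in, so what non-compliance costs that test cannot be read from 12.2.

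**Working it through.** **1. When can a man first be a complier?**
- Denominator 88: 12 (weeks 1-4) + 64 (weeks 5-36) + 12 (weeks 37-48).
- 80% of 88 = 70.4, so 71 sessions are needed.
- 12 are done by week 4, then two a week: (71 - 12)/2 = 29.5, so the 71st falls in week 34.
- Section 6.1 allows flexibility. At three supervised sessions a week throughout, 71/3 = 23.7, which is week 24.
- If one session in each of Cycles 12-23 also counted, the denominator would be 100 and 80 would be needed. With 76 done by week 36 and one a week after that, the 80th falls in week 40.

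**2. How many men die before then?** Control median 33.5 months, exponential (12.2): hazard = ln 2/33.5 = 0.0207 a month. Week 34 is 7.82 months. Deaths by then: 1 - exp(-0.0207 x 7.82) = 14.9%.

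**3. Size of the artefact with no true effect.**
- Rough check: with 36 months' uniform accrual and at least 36 months' follow-up, the control death probability is 0.665. Compliers have no deaths before week 34 and the control hazard after it. Weighting by control deaths, the average HR is about (0.665 - 0.149)/0.665 = 0.78.
- Simulation: 433 per arm, 36+36 months, every planned session attended while alive, compliers v all controls, OS from randomisation. The lower first-year hazards are assumptions; later hazard is raised to hold the median at 33.5 months.

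| First-year hazard | Deaths by week 34 | Null HR, week 34 | False significant benefit (nominal 2.5%) | Null HR, week 24 |
|---|---|---|---|---|
| Constant (plan) | 15% | 0.78 | about 78% | 0.84 |
| Half | 8% | 0.89 | 26-31% | 0.92 |
| Quarter | 4% | 0.94-0.95 | 9-12% | 0.96 |

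The ranges span repeated simulation runs. With 60-month accrual the week-34 HRs are 0.80, 0.90 and 0.95. A landmark at 48 weeks, with attendance unrelated to prognosis, brings the null HR back to 0.99-1.00.

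**4. Power.** Take the SE of log HR as sqrt(1/d0 + 1/d1), two-sided 0.05. Event probabilities at 36+36 months are 0.665 (control) and 0.576 (HR 0.78).
- The plan's 80%: d0 = 274.1, d1 = 237.2, SE = 0.0887; 0.2485/0.0887 - 1.96 = 0.84, power 80.0%. Reproduced.
- The plan's 77.7%: d1 = 371 x 0.576 = 213.6, SE = 0.0913; 0.2485/0.0913 - 1.96 = 0.76, power 77.7%. Reproduced.
- ITT with 10% non-compliers kept in: log HR = (0.9 + 0.1b) x ln 0.78, where b is the share of benefit they keep. For b = 0, HR = 0.80, d1 = 240.9, SE = 0.0883; 0.2236/0.0883 - 1.96 = 0.57, power 71.6%.

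| Benefit kept by non-compliers | ITT power, 36-month accrual | ITT power, 60-month accrual |
|---|---|---|
| None | 71.6% | 75.8% |
| Half | 76.0% | 80.0% |
| All | 80.0% | 83.8% |
| Complier comparison (371 v 412) | 77.7% | 81.7% |

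At 36 months the ITT power is below 77.7% unless non-compliers keep about 70% of the benefit.

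**The case against.** **The bias depends on an implementation the plan does not state.** This is true. Section 12.11.3 names neither endpoint nor comparator, and a dose-response question could be asked within the exercise arm. But 12.4 ties sessions completed to OS, and the stated definitions lead to the biased comparison unless something is added. The sizes above cover only compliers against all controls, the comparator that 12.2 uses for its power figure. A within-arm analysis by sessions completed has the same problem, but its size was not computed.

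**The denominator is not fixed.** A reader might infer that 88 holds for every man. The text does not go that far: 6.1 attaches an adverse-event condition, and the plan does not say whether planned sessions fall for men who are limited by events or who die. If only sessions scheduled while alive counted, the guaranteed survival time would go. Counting the sessions from Cycle 12 would lengthen it.

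**Section 12.2 does give ITT power.** It does: 80% for 412 v 412. A reader might conclude that ITT power is missing altogether, or that 77.7% is a miscalculation; neither holds. The 77.7% reproduces and is openly described as a complier comparison. If 0.78 is meant as the ITT effect, imperfect adherence is already inside it and no deduction from 80% is due. The plan does not say which it is, although it keeps 0.78 for compliers.

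**Non-compliers may keep much of the benefit.** They may. Section 6.1.5 lets guided self-managed exercise stand in for a supervised session ("a self-managed session replacing a supervised session in this way must be recorded in REDCap") yet counts only in-person sessions as attendance. That is a reason to state the assumption.

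**These are secondary analyses.** They are. Nothing here biases the primary ITT comparison.

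**Conclusion.** The main point holds as a gap in specification. Applied as written to OS from randomisation, the attendance rule can produce a false survival benefit. For compliers against all controls, with 88 planned sessions and full attendance while alive, the null HR is about 0.78 under the plan's own constant hazard, as large as the effect the trial is designed to detect. It is about 0.89 or 0.94-0.95 if first-year hazard is half or a quarter. Entry is restricted to low or intermediate risk, which makes lower early mortality plausible, so 0.78 should not be read as the expected size.

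The power point also holds, more narrowly: no ITT power under non-compliance is given. If 0.78 is the full-compliance effect, 10% non-compliance costs the ITT test 0 to 8 points from 80% at 36-month accrual, depending on an assumption the plan leaves out.

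**What to change.** **Sections 12.4 and 12.11.3.** Name the endpoint, the comparator and the sessions that form the denominator, including how adverse events and the sessions from Cycle 12 are treated. For OS, do one of the following:
- start at a landmark at the end of the supervised period (Cycle 12 Day 1, or the end of Year 1 if make-up sessions count to then), include only men alive at that point in each group compared, and count attendance only up to it; or
- model attendance as time-dependent.

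Label the result as non-randomised.

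**Section 12.2.** State whether 0.78 is the ITT or the full-compliance effect. Replace 77.7%, or accompany it, with the ITT power under stated assumptions about non-compliers, for example no benefit and half. Reconcile the 36-month enrolment with the 60 months in the synopsis and the 5 years in 17.6.

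**Cost.** Wording only; attendance is already recorded. The stated power may look less favourable. Early deaths leave the landmark analysis: about 20% of men by week 48 under constant hazard (1 - exp(-0.0207 x 11.04)), fewer if early mortality is lower. Healthy-adherer selection remains, because fitter men attend more, and the landmark does not remove it.

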12.12 Interim Analyses

We are planning a feasibility study and three interim analyses: one for effectiveness, one for efficacy, and one for accrual. All interim data will be reviewed by the GAP4 steering committee and Data Monitoring Committee.

Feasibility study

The conduct of the study is dependent on patient willingness to participate in the study and compliance with the assigned intervention strategy, as well as the site's ability to provide the recommended intervention. We will start the trial at 1 site in advance of the GAP4 kick-off meeting (slated for early December 2015/early January 2016), and summarise challenges, lessons learned, and study updates from this pilot phase at the kick-off meeting.

Analysis 1: Effectiveness of the intervention

This futility analysis will determine whether the intervention has an effect on exercise parameters related to fitness and physical function, specifically measured by leg extensions and the 400m walk test. A change in these measurements between study arms will be based on the first 15% of patients (N=130) completing the first 6 months of the intervention phase. Data provided by [name] on observed group differences at 3 months in the first few patients in a similar trial, showed leg extensions to be improved by 6.26kg (average standard deviation (SD) 5.16, and 400m walk by 12.5 seconds, average SD 8.75, which represents effect sizes of 1.21 and 1.43, respectively. Unfortunately, due to small sample size, the confidence intervals around these effect sizes are quite wide.

	mean diff	SD (approx.)	estimated effect size	95% confidence interval
400m Walk	-12.52	8.75	1.43	(-0.48, -2.39)
Leg Extension	6.26	5.16	1.21	(0.33, 1.95)

We will complete this interim analysis when the first 130 patients complete 1RM and 400m walk testing on or within 7 days *after* Cycle 6, Day 1 (6 months after Day 1 of the intervention), and estimate the mean difference between the groups for both the 400m walk and leg extensions. [name] data is pilot data based on small sample sizes, so we have attenuated the expected effect size for these two parameters to 0.40; however, we will revisit the comparison when a larger dataset is available. We will consider an analysis similar in scope to this example: Assuming that the standard deviation of change in 400m walk is 8.75 and leg extension is 5.16 (based on preliminary data above), if the difference in leg extension strength between the two arms is less than 2.06kg *or* the difference in the 400m walk between the two arms is less than 3.5 seconds we will consider modifications to the protocol.

Analysis 2: Efficacy and possible early termination due to unequivocal results

The interim analysis plans to investigate the primary outcome when half of the required number of events for final analysis of overall survival (i.e., 315 events) will be carried out with $\alpha=0.0005$. A stringent alpha level has been chosen to reduce the amount of alpha spending prior to the final analysis with the full sample. The interim analyses will spend 0.001 of the 0.05 alpha requiring us to reach $0.05-0.001 = 0.049$ for the final trial results to be considered statistically significant with an overall $\alpha=0.05$.

The interim analysis will be carried out to assess whether the study should terminate early due to an unequivocal result at the 0.0005 level. This interim analysis can result in recommendations that include modifications to the study, including termination of accrual, modifications to data collection, or early reporting of results. Recommendations will be made to the Steering Committee, who will make the final decisions.

The interim analysis will describe the limits of the effect size seen between the two arms of the study on overall survival. The limits will be calculated using a Cox proportional hazards regression model and use a two sided $(1-0.001) = 99.9\%$ confidence interval. If this confidence interval excludes a 22% or higher reduction in mortality or excludes 1 (no difference between the groups) the trial will already show a statistically significant finding with $p < 0.001$. If the confidence interval does not contain a 22% increase in survival it is unlikely that exercise improves survival sufficiently to warrant the continuation of the study. Or if the confidence interval does not contain 1 it may be considered unethical to continue to randomise patients to the control arm. If this is the case, the results will be reported to the Steering Committee with a Kaplan Meyer plot to illustrate these findings, and the Steering Committee will make the final decision.

Analysis 3: Accrual assessment

The Steering Committee and Data Monitoring Committee will receive notification every 3 months of the interim and total accrual. We will request that all sites keep monthly accrual data to ensure complete data for this assessment. This would include number of patients who were invited to participate, interested, completed exercise screening days, and enrolled. The Steering Committee and Research Advisory Committee will make final decisions about expanding eligibility criteria, exploring alternative options, etc.

